**16 HOW SUPPLIED/STORAGE AND HANDLING**

**16.1 How Supplied**

- Vial, 1 dose (0.5 mL) - (NDC number: 43528-002-01)
- Package of 5 single dose vials - (NDC number: 43528-002-05)
- Prefilled syringe, 1 dose (0.5 mL) - (NDC number: 43528-003-01)
- Package of 5 single dose prefilled syringes - (NDC number: 43528-003-05)

The tip caps and stoppers of the prefilled syringes and vial stoppers are not made with natural rubber latex.

**16.2 Storage Conditions**

Store in a refrigerator at 2°C to 8°C (35°F to 46°F).

Do not freeze; discard if the vaccine has been frozen.

Do not use the vaccine after the expiration date shown on the vial or prefilled syringe label.

**17. PATIENT COUNSELING INFORMATION**

- Inform vaccine recipient of the potential benefits and risks associated with vaccination, as well as the importance of completing the immunization series.
- Emphasize that HEPLISAV-B contains non-infectious purified HBsAg and cannot cause hepatitis B infection.
- Advise vaccine recipient to report any adverse events to their healthcare provider or to the Vaccine Adverse Event Reporting System (VAERS) at [name] and [www.vaers.hhs.gov](http://www.vaers.hhs.gov).
- Provide the Vaccine Information Statements, which are available free of charge at the Centers for Disease Control and Prevention (CDC) website ([www.cdc.gov/vaccines](http://www.cdc.gov/vaccines)).

© 2018, Dynavax Technologies Corporation.  
All rights reserved.

Manufactured by:  
Dynavax Technologies Corporation  
Berkeley, CA 94710 USA

US-18-00-00015

**APPENDIX 3: TOXICITY GRADING SCALE FOR HEALTHY ADULT AND ADOLESCENT VOLUNTEERS ENROLLED IN PREVENTIVE VACCINE CLINICAL TRIALS**

Local Reaction to Injectable Product	Mild (Grade 1)	Moderate (Grade 2)	Severe (Grade 3)	Potentially Life Threatening (Grade 4)
Erythema/Redness a	2.5 – 5 cm	5.1 – 10 cm	> 10 cm	Necrosis or exfoliative dermatitis
Induration/Swelling b	2.5 – 5 cm and does not interfere with activity	5.1 – 10 cm or interferes with activity	> 10 cm or prevents daily activity	Necrosis
Pain	Does not interfere with activity	Repeated use of non-narcotic pain reliever > 24 hours or interferes with activity	Any use of narcotic pain reliever or prevents daily activity	Emergency room (ER) visit or hospitalization
Fever c (°C) (°F)	38.0 – 38.4 100.4 – 101.1	38.5 – 38.9 101.2 – 102.0	39.0 – 40 102.1 – 104	> 40 > 104
Malaise	Uneasiness or lack of well being	Uneasiness or lack of well being; limiting instrumental ADL	A grade is not available	A grade is not available
Headache	No interference with activity	Repeated use of non-narcotic pain reliever > 24 hours or some interference with activity	Significant; any use of narcotic pain reliever or prevents daily activity	ER visit or hospitalization
Myalgia	No interference with activity	Some interference with activity	Significant: prevents daily activity	ER visit or hospitalization
Fatigue	No interference with activity	Some interference with activity	Significant: prevents daily activity	ER visit or hospitalization

Sources: ([Center for Biologics Evaluation and Research 2007](#), [National Cancer Institute 2010](#)).

a In addition to grading the measured local reaction at the greatest single diameter, the measurement should be recorded as a continuous variable.

b Induration/swelling should be evaluated and graded using the functional scale as well as the actual measurement.

c Oral temperature; no recent hot or cold beverages or smoking. Subject should be at rest for vital sign measurements.

## APPENDIX 4: LIST OF ADVERSE EVENTS OF SPECIAL INTEREST

Each subject will be assessed for these autoimmune, hypersensitivity, and inflammatory diseases during the trial. The following AESIsa will be evaluated and reported to FDA:

### Gastrointestinal disorders

- Celiac disease
- Crohn's disease
- Ulcerative colitis
- Ulcerative proctitis

### Liver disorders

- Autoimmune cholangitis
- Autoimmune hepatitis
- Primary biliary cirrhosis
- Primary sclerosing cholangitis

### Metabolic diseases

- Addison's disease
- Autoimmune thyroiditis (including Hashimoto thyroiditis)
- Diabetes mellitus type 1
- Grave's or Basedow's disease

### Musculoskeletal disorders

- Antisynthetase syndrome
- Dermatomyositis
- Juvenile chronic arthritis (including Still's disease)
- Mixed connective tissue disorder
- Polymyalgia rheumatic
- Polymyositis
- Psoriatic arthropathy
- Relapsing polychondritis
- Rheumatoid arthritis
- Scleroderma, including diffuse systemic form and CREST syndrome
- Spondyloarthritis, including ankylosing spondylitis, reactive arthritis (Reiter's Syndrome) and undifferentiated spondyloarthritis
- Systemic lupus erythematosus
- Systemic sclerosis

Neuroinflammatory disorders

- Acute disseminated encephalomyelitis, including site specific variants: eg, non-infectious encephalitis, encephalomyelitis, myelitis, myeloradiculomyelitis
- Cranial nerve disorders, including paralyses/paresis (eg, Bell's palsy)
- Guillain-Barré syndrome, including Miller Fisher syndrome and other variants
- Tolosa Hunt syndromeb
- Immune-mediated peripheral neuropathies and plexopathies (including chronic inflammatory demyelinating polyneuropathy, multifocal motor neuropathy and polyneuropathies associated with monoclonal gammopathy)
- Multiple sclerosis
- Myasthenia gravis, including Eaton-Lambert syndrome
- Narcolepsy
- Optic neuritis
- Transverse Myelitis

Skin disorders

- Alopecia areata
- Autoimmune bullous skin diseases (including pemphigus, pemphigoid and dermatitis herpetiformis)
- Cutaneous lupus erythematosus
- Erythema nodosum
- Morphoea
- Lichen planus
- Psoriasis
- Rosacea
- Sweet's syndrome
- Vitiligo

Vasculitides

- Large vessels vasculitis including: giant cell arteritis such as Takayasu's arteritis and temporal arteritis
- Medium sized and/or small vessels vasculitis including: polyarteritis nodosa, Kawasaki's disease, microscopic polyangiitis, Wegener's granulomatosis, Churg-Strauss syndrome (allergic granulomatous angiitis), Buerger's disease (thromboangiitis obliterans), necrotizing vasculitis and anti-neutrophil cytoplasmic antibody (ANCA) positive vasculitis (type unspecified), Henoch-Schonlein purpura, Behcet's syndrome, leukocytoclastic vasculitis

Others

- Antiphospholipid syndrome
- Autoimmune hemolytic anemia
- Autoimmune glomerulonephritis (including IgA nephropathy, glomerulonephritis rapidly progressive, membranous glomerulonephritis, membranoproliferative glomerulonephritis, and mesangioproliferative glomerulonephritis)
- Autoimmune myocarditis/cardiomyopathy
- Autoimmune thrombocytopenia
- Goodpasture syndrome
- Idiopathic pulmonary fibrosis
- Pernicious anemia
- Raynaud's phenomenon
- Sarcoidosis
- Sjögren's syndrome
- Stevens-Johnson syndrome
- Uveitis

a List provided to Dynavax Technologies by FDA on 30 January 2019

b Added by Dynavax

FDA	United States Food and Drug Administration
GMC	geometric mean concentration
GRF	glomerular filtration rate
HBV	hepatitis B virus
MAE	medically-attended adverse event
MedDRA	Medical Dictionary for Regulatory Activities
mITT	modified intent-to-treat (population)
ODS	output delivery system
PT	Preferred Term
SAE	serious adverse event
SAP	statistical analysis plan
SD	standard deviation
SOC	System of Organ Class
SPR	seroprotection rate
TEMAE	treatment emergent medically-attended adverse event
TFL	tables, figures, listings

Abbreviation or Term	Definition
WHO	World Health Organization

1.0 INTRODUCTION

This statistical analysis plan contains definitions of analysis populations and endpoints, outlines the timing of statistical analyses, and provides a comprehensive description of statistical analyses to be implemented to assess the safety and immunogenicity in patients on hemodialysis as described in Protocol DV2-HBV-24 (Amendment 4: 17 April 2020): “An Open-label, Single Arm Study, Evaluating the Immunogenicity and Safety of HEPLISAV-B® in Adults With End-Stage Renal Disease Undergoing Hemodialysis”.

2.0 STUDY OVERVIEW

[REDACTED]

[REDACTED]

[REDACTED]

[REDACTED]

In this study, the safety and immunogenicity in patients on hemodialysis will be evaluated further to investigate an optimal dosing regimen for this patient population. An optimal dosing regimen for HEPLISAV B that induces higher rates of protection, earlier onset of protective immunity, and longer duration of protection in hemodialysis patients would be an important advance in vaccine development given the ongoing risk of HBV infection in the hemodialysis setting and consequences of HBV infection in this highly compromised patient population.

This study will consist of a 4-injection (0.5 mL per injection) regimen of HEPLISAV-B at Weeks 0, 4, 8, and 16. It is anticipated that a fourth dose of HEPLISAV-B will provide improved seroprotection [REDACTED] for hemodialysis patients. Eligible subjects will receive HEPLISAV-B at Weeks 0, 4, 8 and 16 and will be followed through Week 68 (Figure 2-1). The study is designed to evaluate the immunogenicity over the 20-week period and safety over the 68-week period.

Figure 2-1: Study Flow Diagram

	Screening	HEPLISAV-B Treatment	Follow-Up						
Day:	-28		1	29	57	113	141	197	295 477
Week:	-4		0	4	8	16	20	28	42 68
	N = 100		X	X	X	X			

X = study injection

For the primary immunogenicity endpoint, SPR will be evaluated at Week 20, 4 weeks after the last injection, [REDACTED]
[REDACTED]

3.0 STUDY OBJECTIVES

3.1 Primary Objectives

- To evaluate the safety of HEPLISAV-B with respect to clinically significant adverse events
- To evaluate the immunogenicity induced by HEPLISAV B at Week 20 as measured by the seroprotection rate (SPR)

3.2 Secondary Objectives

- To evaluate the immunogenicity of HEPLISAV-B as measured by the percentage of subjects with anti-HBs concentration ≥ 100 mIU/mL
- To evaluate the immunogenicity of HEPLISAV-B as measured by the anti HBs geometric mean concentration (GMC)
- To evaluate the immunogenicity of HEPLISAV-B at each study visit through 20 weeks after the first dose of study vaccine as measured by the SPR

4.0 ANALYSIS VARIABLES

Primary Endpoints

- Proportion of subjects with treatment-emergent MAEs
- Proportion of subjects with treatment-emergent SAEs, acute myocardial infarctions (AMIs), or deaths
- Proportion of subjects with treatment-emergent immune-mediated adverse events of special interest (AESIs)
- SPR at Week 20

Secondary Endpoints

- Proportion of subjects with anti-HBs concentration ≥ 100 mIU/mL
- Anti-HBs geometric mean concentration (GMC)
- SPR at each study visit through 20 weeks after the first dose of study vaccine

5.0 SAMPLE SIZE CONSIDERATIONS

The sample size calculation is based on approximately 100 subjects in the per-protocol population. With an expected 15% loss to follow up prior to week 20, approximately 115 subjects will be enrolled. This sample size would allow estimating immunogenicity response at the following accuracy levels depending on the observed immunogenicity responses (Table 5-1).

Table 5-1: Sample Size Estimates

N	If Observed Immunogenicity Response is	Width of the Resulting 95% Confidence Interval ^a	Lower Limit of the Resulting 95% Confidence Interval ^a
100	80.0%	0.165	70.8%
100	86.0%	0.145	77.6%
100	90.0%	0.127	82.4%
100	95.0%	0.096	88.7%

N = number of subjects

^a Calculation based on exact method (Clopper-Pearson)

Note: Approximately 115 subjects will be enrolled to meet the N of 100 evaluable subjects in the per-protocol population.

6.0 ANALYSIS POPULATIONS

6.1 Enrolled Population

The enrolled population is defined as all patients who enrolled in the study.

6.2 Safety Population

The safety population will comprise all subjects who received at least 1 study injection, excluding subjects who have no on-study safety data.

6.3 Efficacy Population

The per-protocol (PP) population for the immunogenicity analysis will comprise all subjects who receive all study injections, have no major protocol deviations (see Section 9.2), and have anti-HBs levels obtained within the study visit window at Week 20. PP population is defined for Week 20 visit, but will be used in analyses at other visits where applicable.

The modified intent-to-treat (mITT) population for the immunogenicity analysis will comprise all eligible subjects who receive at least 1 study injection and have at least 1 post-injection immunogenicity evaluation.

7.0 DEFINITIONS, COMPUTATIONS, AND CONVENTIONS

7.1 Definitions and Computations

Study Day

Study day will be calculated in reference to the date of first injection (Day 1). For visits conducted on or after the first injection date, study day is calculated as (visit date – first injection date + 1). For visits conducted before the first injection date, study day is calculated as (visit date – first injection date). There will be no Day 0.

Date of First Injection and Date of Last Injection of Study Vaccine

The date of the first injection of study vaccine is defined as the date a patient receives the first injection of the study vaccine. The date of the last injection of study vaccine is the date a patient receives the last injection of the study vaccine.

Treatment-Emergent Period

In this trial, only medically attended adverse events (MAEs), AEs for which a subject seeks medical attention at a doctor's office, clinic, study site, emergency room, or is hospitalized, will be collected.

The reporting period for all non-serious MAEs begins at the time of the first study injection (Day 1) through EOS Visit. All MAEs will be captured on the MAE eCRF.

Any SAE that occurs from the time the consent is signed through EOS Visit, whether or not the SAE is related to the study treatment, must be reported.

The treatment-emergent period is defined as time from the first study injection through EOS visit.

7.2 Conventions

Unless otherwise specified, the following conventions will be applied to all analyses:

- 1 year = 365.25 days. Year is calculated as (days/365.25) rounded up to 1 significant digit.
- 1 month = 30.4375 days. Month is calculated as (days/30.4375) rounded up to 1 significant digit.
- Age will be calculated by the following SAS code:

If only year of birth is given, then Age = (Year of Screening – Year of Birth). Otherwise

```
age = floor ((intck('month', birth_date, consent_date) -  
(day(consent_date) < day(birth_date))) / 12);
```

- 1 pound = 0.454 kg
- 1 inch = 2.54 cm
- Missing safety data will not be imputed unless otherwise specified.
- For immunogenicity results, anti-HBs concentrations, are obtained using the Elecsys Anti-HBs II assay. For concentration reported as <value, half of the value will be used in calculation. For concentration reported as >value, value+1 will be used in calculation.
- For safety analyses, percentages will be calculated based on the number of patients in the analysis population.

- For by-visit observed data analyses, percentages will be calculated based on the number of patients with nonmissing data as the denominator unless otherwise specified.
- For other continuous endpoints, the summary statistics will include mean, standard deviation, median, and range (minimum and maximum).
- For categorical endpoints, the summary statistics will include counts and percentages.
- MAEs and medical history will be coded using the Medical Dictionary for Regulatory Activities (MedDRA) version 17 or higher.
- Prior therapies and concomitant medications will be coded using the World Health Organization (WHO) Drug Dictionary.

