## **9.3 Immunogenicity Assessments**

Serum sample will be obtained for anti-HBs measurements at baseline and then at Weeks 4, 8, 16, and 20.

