#### **9.4.3 Safety Laboratory Assessments**

Laboratory assessments are listed below and will be performed according to the Schedule of Study Assessments ([Appendix 1](#)). Sample collections will be prior to injection on vaccination days. Laboratories obtained within 7 days of Day 1 visit do not need to be repeated on Day 1.

- Serum chemistry and hematology will be performed at Screening by a central laboratory.
- Hepatitis and HIV testing at Screening Visit by a central laboratory: serum hepatitis B, hepatitis C, and HIV testing by laboratory tests for HBsAg, anti-HBc, anti-HBs, anti-HCV, and anti-HIV-1/2, respectively
- Reserve serum and plasma aliquot specimens will be collected and stored frozen for possible future testing.
- Additional details for specific tests are provided in the Laboratory Manual.

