9.0 STATISTICAL METHODS

This is an open-label, single arm study, evaluating the immunogenicity and safety of HEPLISAV-B® in adults with end-stage renal disease undergoing hemodialysis. No pre-specified hypothesis testing will be performed. All analyses of demographics and baseline

characteristics, medical history, vaccine exposure, immunogenicity and safety will be summarized in a descriptive manner.

All confidence intervals are two-sided 95% confidence intervals unless otherwise specified.

In general, continuous variables will be summarized by sample size, mean, standard deviation, median, quartiles, minimum and maximum, and categorical variables will be summarized by counts and percentages. All data processing, summarization, and analyses will be performed using SAS Version 9.3 or higher. Specifications for tables, graphs, and data listings will be provided in the tables, figures, listings (TFL) specifications document if needed.

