9.6 Immunogenicity Analyses

Immunogenicity data will be analyzed based on the PP population by visit for all visits through 20 weeks with immunogenicity data collected.

The SPR will be estimated. The associated 2-sided 95% confidence interval will be calculated using the Clopper-Pearson method.

Proportion of subjects with anti-HBs concentration ≥ 100 mIU/mL and associated 2-sided 95% confidence interval will also be calculated using Clopper-Pearson methods.

Anti-HBs geometric mean concentration (GMC) and associated 2-sided 95% confidence interval will be calculated by exponentiating the mean and confidence interval in \log_{10} of the anti-HBs concentration assuming Normal distribution.

Analyses based on the mITT population may also be conducted.

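### Does setting anti-HBs results above the assay limit to value+1 distort the GMC enough to need a change?

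*SAP*

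**What the plan says.** SAP 7.2 names the assay (Elecsys Anti-HBs II) and sets one convention for each end of its range. At the top: "For concentration reported as >value, value+1 will be used in calculation". At the bottom: "For concentration reported as <value, half of the value will be used in calculation". Under SAP 9.6 the GMC and its two-sided 95% interval "will be calculated by exponentiating the mean and confidence interval in" log10 concentration, with Normality assumed. SAP 4.0 lists the GMC as a secondary endpoint.

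SAP 9.0 adds that "No pre-specified hypothesis testing will be performed", and that in general "continuous variables will be summarized by sample size, mean, standard deviation, median, quartiles, minimum and maximum". Samples are taken at baseline and Weeks 4, 8, 16 and 20 (Protocol 9.3). Neither document gives the assay's limits or a rule for diluting and retesting high samples. On laboratory tests, Protocol 9.4.3 says: "Additional details for specific tests are provided in the Laboratory Manual".

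**The concern.** Adding 1 mIU/mL to a large limit changes nothing on a log scale, so the rule amounts to a cap. A cap lowers the mean and cannot raise the variance. Taken alone, it pulls the GMC down and narrows its interval, and the method in SAP 9.6 does not know that some values were replaced.

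Four injections are meant to produce high concentrations, and Protocol 2.1 links duration of protection to the peak antibody level. The upper tail is therefore part of what the GMC should show. With no limits, no counts beyond them and no sensitivity analysis in the SAP, a reader might be unable to tell a sound GMC from a compressed one. The suggested remedy was to report the counts and add a GMC from a censored lognormal model.

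**Working it through.** **Inputs from the documents.** The two substitution rules (SAP 7.2), the log10 t-interval (SAP 9.6), and about 100 per-protocol subjects (SAP 5.0). The plan gives no figure for the GMC. SAP Table 5-1 concerns the seroprotection rate (SPR) only; its Clopper-Pearson widths recompute to 0.1652, 0.1450, 0.1272 and 0.0964, matching the printed values.

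**Assumed, because the documents are silent.** The share f above the upper limit U, the SD of log10 concentration, and the share of non-responders.

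**Step 1: the +1.** (U+1)/U is 1.001 at U = 1,000 and 1.0001 at U = 10,000. The rule is a cap at U.

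**Step 2: the cap alone, one Normal distribution, SD 1.0.** With c the standard Normal quantile at 1−f and φ the Normal density, the mean of log10 concentration shifts by d = −φ(c) + c·f, and the GMC ratio is 10^d. At f = 20%: c = 0.8416, φ(c) = 0.2800, d = −0.2800 + 0.1683 = −0.1116 (unrounded inputs), ratio 0.773. The coverage column comes from 20,000 simulated trials of 100 subjects.

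| Share above limit | GMC ratio | CI width ratio | Coverage of 95% CI |
|---|---|---|---|
| 5% | 0.953 | 0.957 | 0.947 |
| 10% | 0.897 | 0.915 | 0.926 |
| 20% | 0.773 | 0.833 | 0.755 |
| 30% | 0.645 | 0.751 | 0.276 |

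This is the alarming version, but it is not the SAP's procedure. It leaves out the lower rule and assumes that everyone responds.

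**Step 3: both SAP rules, with non-responders.** Table 5-1 plans around SPRs of 80% to 95%, so 5% to 20% not seroprotected. Assume 10% non-responders with log10 concentration N(0, 0.4), responders N(2.9, 0.7), and a lower limit of 2 mIU/mL.

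- Upper rule: the share of responders above U is q = f/0.9, and the shift is 0.9 × 0.7 × (−φ(c) + c·q), with c now the quantile at 1−q. At f = 20%: q = 0.2222, c = 0.7647, φ(c) = 0.2978, bracket −0.1279, shift −0.0806.
- Lower rule: results under 2 become 1, which is 0 on the log10 scale. The limit lies 0.301/0.4 = 0.753 SD above the non-responder mean, so the shift is +0.10 × 0.4 × φ(0.753) = +0.0120.
- Net: −0.0806 + 0.0120 = −0.0686, ratio 0.85.

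The same steps give 0.99 at 5%, 0.95 at 10% and 0.75 at 30%. A 400-trial simulation gave 1.00, 0.95, 0.87 and 0.75 at 5, 10, 20 and 30%. Its coverage was 0.96 at 10%, 0.92 at 20% and 0.78 at 30%. The Monte Carlo SE at 20% is √(0.92 × 0.08/400) = 0.014. Other runs of the same setting gave 0.92 to 0.93 at 20% and 0.74 to 0.76 at 30%.

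**Step 4: would the censored model do better?** If one Normal distribution holds, yes: its GMC stays within 0.98 to 1.02 of the truth. In the Step 3 population it overshoots, with ratios of 1.07, 1.18 and 1.32 at 10, 20 and 30% above the limit. It reads the non-responders as spread and extrapolates the upper tail too far. At 20% above the limit, the root mean square error on log10 was:

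| Non-responders | SAP rule | Censored lognormal |
|---|---|---|
| 10% | 0.113 to 0.115 | 0.133 to 0.146 |
| 20% | 0.128 | 0.174 |

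With 10% or 20% non-responders the SAP rule had the smaller error at every share tested.

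**Step 5: other endpoints.** Seroprotection is anti-HBs of at least 10 mIU/mL. Replacing a result beyond either limit leaves that classification unchanged if the lower limit is no more than 10 and the upper limit no less than 10. The proportion at or above 100 mIU/mL is safe if the upper limit is at least 100.

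**The case for a change.** The case for a change is that the direction of the bias is a mathematical fact, the SAP does not say how many values are replaced, and a few sentences would cure that. SAP 9.0 promises medians and quartiles only in general, while SAP 7.2 gives a list for other continuous endpoints that omits quartiles, so their appearance for anti-HBs is not certain. The censored model is not useless either. With 5% non-responders and at least 20% above the limit it had the smaller error. With 10% non-responders and 30% above, its coverage was better (0.87 against 0.78).

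The direction stands, and so does the point about counts. But nothing in the documents shows that any result will exceed the limit, and diluting high samples to an end value would largely remove the issue. The limits and any dilution rule may sit in the Laboratory Manual, and the contents of tables and listings are in a separate document (SAP 12.0 to 14.0). Under the general summaries in SAP 9.0, a maximum at the limit plus 1 would reveal capping, and a third quartile there would show that about a quarter or more of results were capped. The median is untouched while fewer than half exceed the limit. These summaries would not size a capped share of 10% to 20%; a count would, and an analyst can supply one from the existing data without altering any planned estimate.

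**Conclusion.** No change to the plan. The SAP fixes a simple, visible convention for each tail in advance. The effect is small while no more than about 10% of results exceed the upper limit: about 5% on the GMC under both rules with 10% non-responders, or about 10% for the cap alone at SD 1.0. It becomes material only from about 20%, at roughly 15% too low, and 25% too low at 30%. All of these shares, SDs and mixtures are assumptions, since the documents give none of them.

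The upper cap errs against the vaccine, on a secondary descriptive endpoint with no comparator and no test. The Week 20 SPR does not move. The proposed censored analysis exchanges an understatement for an overstatement of similar size wherever there is a distinct non-responder group, so it is a debatable choice and not a better method. The missing limits and counts are reporting detail that analysts would normally put in a table footnote.
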